4.3. Justification for Dose

This study will use a vibegron dose of 75 mg QD, which is the same dose used for the pivotal Phase 3 study of OAB in men and women (RVT-901-3003) and the associated long-term Phase 3 extension study (RVT-901-3004) as well as in the parent OAB/BPH study, URO-901-3005.

4.4. End of Study Definition

The end of the study is defined as the date that the last subject has completed the study (ie, through the Week 52 Visit), discontinued from the study, or is lost to follow-up.

5. Study Population

The study is being conducted in men with OAB symptoms while receiving pharmacological therapy for BPH who have completed vibegron Study URO-901-3005. Specific inclusion and exclusion criteria are specified below. Prospective approval of protocol deviations to recruitment and enrollment criteria, also known as protocol waivers or exemptions, is not permitted.

Eligibility for Study URO-901-3006, including blood pressure thresholds, should be confirmed at the Week 24 visit (Visit 11) of Study URO-901-3005. For laboratory assessments, the most recent results available from Study URO-901-3005, including those from Week 24, may be used to confirm eligibility. The subject should be enrolled into Study URO-901-3006 within 7 days of completing the Week 24 visit from Study URO-901-3005.

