1.3. Schedule of Assessments

Day/Week	Open-Label Treatment				
	Visit 11	Visit 12	Visit 13	Telephone Call	Visit 14 or Early WD
Day/Week	Week 24 (Day 169) ^a	Week 28 (Day 197)	Week 36 (Day 253)	Week 44 (Day 308)	Week 52 or Early WD (Day 365)
Visit Window	±4 days	± 4 days	± 4 days	± 4 days	± 4 days
Informed Consent	X				
Subject Entry into IWRS	X				
Inclusion and Exclusion Criteria Review ^a	X				
AE/SAE Review	†	X	X	X	X
Concomitant Medication Review	†	X	X	X	X
IPSS ^b	†		X		X
[REDACTED]					
PGI ^b	†				X
[REDACTED]					
Vital Signs ^c	†	X	X		X
Brief Physical Examination	†				X
PVR volume	†	X	X		X
Laboratory Assessments ^d	†		X		X
Review and Data Enter Completed Bladder Diary ^e	†	X	X		X
Dispense Bladder Diary	X	X	X		
Dispense Open-label Study Drug	X	X	X		

AE = adverse event; [REDACTED] IPSS = International Prostate Symptom Score; IWRS = interactive web response system; OAB = overactive bladder; [REDACTED] PGI = Patient Global Impression; PRO = patient-reported outcomes; PVR = Post-void residual; SAE = serious adverse event; WD = withdrawal

- † For noted procedures, the Week 24 (Visit 11) assessments for Study URO-901-3005 serve as initial on-study visit for Study URO-901-3006; these procedures will not be duplicated.
- a Recheck clinical status before enrollment and first dose of open-label study drug. Initiation of Study URO-901-3006 should occur within 7 days of Study URO-901-3005 Week 24/End-of-Study visit.
- b PRO questionnaires should be completed prior to other procedures, including vital signs, blood draws, and study drug dosing.
- c Vital signs (including blood pressure [in triplicate], pulse, body temperature, respiration rate, and weight) should be taken prior to blood draws and study drug dosing.
- d Refer to Section 10.2 for a list of laboratory assessments performed.
- e Subject completes the Bladder Diary PRIOR to each visit.

2. Introduction

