8.4. Adverse Events and Serious Adverse Events

The definitions of an AE or SAE can be found in Section 10.3.

AEs will be reported by the subject (or, when appropriate, by a caregiver, surrogate, or the subject's legally authorized representative).

The investigator and any qualified designees are responsible for detecting, documenting, and recording events that meet the definition of an AE or SAE and remain responsible for following up AEs that are serious, considered related to the study drug or study procedures, or that caused the subject to discontinue the study drug or the study (see Section 7).

8.4.1. Time Period and Frequency for Collecting Adverse Event and Serious Adverse Event Information

All AEs and SAEs will be collected from the signing of the informed consent form through the end of study. In addition, any AEs and SAEs reported within 21 days after the last dose of study drug (5 half-lives of vibegron [half-life approximately 80 hours]) will also be collected. AEs will be collected at the timepoints specified in the Schedule of Assessments (Section 1.3), and as observed or reported spontaneously by study subjects.

Medical occurrences that begin before the start of study drug, but after obtaining informed consent will be recorded in the AE section of the eCRF.

All SAEs (including serious AESIs) will be recorded and reported on the eCRF within **24 hours** of the study site personnel's knowledge of the event, as indicated in Section 8.4.4. Marking the event as "serious" will automatically send required notifications for Sponsor or designee review. The investigator will also submit any updated SAE data within 24 hours of receipt of the information. Nonserious AESIs will be reported on the eCRF within **72 hours** of the site's knowledge of the information

Investigators are not obligated to actively seek AE or SAE information after conclusion of the study participation. However, if the investigator learns of any SAE, including a death, at any time after a subject has been discharged from the study, and he/she considers the event to be reasonably related to the study drug or study participation, the investigator must promptly notify the Sponsor or designee.

The method of recording, evaluating, and assessing causality of AEs and SAEs and the procedures for completing and transmitting SAE reports are provided in Section 10.3.

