9.4.2. Safety Analyses

Safety analysis will be conducted using the SAF-Ext population and summarized by the Vibegron treatment group. The treatment-emergent period will be defined as the period of time from the first dose date of vibegron in this study through 21 days after the last dose of treatment, or the date of initiation of another investigational agent or surgical intervention, whichever occurs first. Safety will be assessed through summaries of adverse events, the frequency of treatment discontinuation due to adverse events, and clinical laboratory evaluations.

AEs will be coded using the latest version of MedDRA (20.0 or higher). The severity of all adverse events will be evaluated by the Investigator. The incidence of adverse events will be presented by system organ class and preferred term, relationship to study treatment and severity.

Laboratory data will consist of chemistry, hematology and urinalysis data. Only data collected by the central laboratory will be included in the analysis.

Descriptive statistics of observed values and change from baseline for vital signs and post void residual urine volume will be listed and summarized.

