10.7.4. Open-label Treatment Period, Telephone Contact (Week 44 [Day 308 ± 4 days])

- Review AEs/SAEs
- Review concomitant medications

10.7.5. Open-label Treatment Period, Visit 14 (Week 52 [Day 365 ± 4 days]) or Early Withdrawal

- Review AEs/SAEs
- Review concomitant medications
- Administer IPSS, [REDACTED], PGI, [REDACTED] scales
- Record blood pressure (3 results taken 1-2 minutes apart after sitting for 5 minutes), pulse, respiration, temperature, and weight
- Perform brief physical examination
- Measure post-void residual volume
- Perform laboratory assessments
- Review and data enter completed Bladder Diary

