
First and last dose of vibegron refer to the first and last dose across both study URO-901-3005 and URO-901-3006, for subjects who were treated with at least one dose of vibegron in study URO-901-3006.
 
EOS: End of study is defined as the date when the subject has completed one of the following: completes Week 52 Safety Follow-up, discontinued from the study, or is lost to follow-up.
 
*AEs with a start date equal to the date of first dose of vibegron will be considered treatment-emergent unless the relatedness to study drug is marked ‘Not applicable’.
 
Overlapping period: Medication start date \leq period start date < medication end date, medication start date < period end date \leq medication end date, or period start date \leq medication start or end date < period end date, then the medication is considered overlapping with the period.
			

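### No AE enquiry is scheduled after the Week 52/Early Withdrawal visit, although the protocol collects AEs and counts them as treatment-emergent for 21 days after the last dose

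*Protocol*

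**What the plan says.** **Collection and analysis window (protocol).** Section 8.4.1 collects AEs and SAEs from consent to the end of the study and, in addition, "any AEs and SAEs reported within 21 days after the last dose of study drug". It explains the 21 days as five half-lives of about 80 hours. Section 9.4.2 runs the treatment-emergent period from the first extension dose "through 21 days after the last dose of treatment", or to an earlier date if the man starts a different trial drug or has an operation.

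**Contacts (protocol).** The last column of the Schedule in Section 1.3 is "Week 52 or Early WD (Day 365"), and the last entry in the visit supplement (Section 10.7.5) is "Open-label Treatment Period, Visit 14 (Week 52 [Day 365 ± 4 days]) or Early Withdrawal". Both include AE review. Nothing follows. Section 4.4 defines the end of the study by the last subject: "The end of the study is defined as the date that the last subject has completed the study (ie, through the Week 52 Visit"), or discontinuation or loss to follow-up.

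**How AEs are found (protocol).** Section 8.4.1 names two routes: the scheduled timepoints, and events observed or spontaneously reported. It adds: "Investigators are not obligated to actively seek AE or SAE information after conclusion of the study participation". Section 8.4.3 follows AEs already reported until about 21 days after the last dose, and SAEs until they resolve, stabilize or are otherwise explained. Section 8.3.4 has clinically significant laboratory values repeated over the same 21 days.

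**SAP.** Table 2 (Section 4.2.4.1) closes the TEAE window at the last dose plus 5 days or the EOS visit, whichever is earlier. Section 7.3 closes it at plus 5 days and does not mention EOS. The Table 2 footnote has a man reach EOS when he "completes Week 52 Safety Follow-up", discontinues or is lost.

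**The concern.** Long-term safety is the primary objective. Within a single at-risk window, the protocol moves from direct questioning at planned contacts to reliance on what is noticed or volunteered. It does so when dosing ends, while its own rationale still treats the man as exposed. An analysis over the full 21 days would mix solicited and unsolicited time, and it would be expected to count fewer new events than a window questioned throughout.

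The 21-day rule is also hard to apply. Section 9.4.2 can close the window early for certain later treatments, but no planned contact would supply those dates. The end-of-study wording in Section 4.4 does not acknowledge that collection runs past the last visit.

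**Working it through.** **1. Window against schedule.** Planned contacts fall on Days 169, 197, 253, 308 (telephone) and 365 (Sections 1.3 and 10.7). For a completer whose last dose is on Day 365, the protocol window ends on Day 365 + 21 = Day 386. The number of planned AE enquiries from Day 366 to Day 386 is 0.

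**2. Length of the gap per man.** If the last dose is *d* days before the final visit, the days of the window left after that visit are 21 − *d*.
- *d* = 0: 21 days.
- *d* = 4 (illustrative assumption): 17 days.

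The same formula applies to a man who withdraws early and attends an Early Withdrawal visit. Section 7.1 calls for that visit after drug is stopped; Section 7.2 qualifies it as done if possible.

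**3. The plan's own 21-day figure.** 5 × 80 h = 400 h, and 400/24 = 16.7 days, so five half-lives do not reproduce 21 days. In the other direction, 21 × 24/80 = 6.3 half-lives. The window covers five half-lives and somewhat more. Assuming simple exponential decay at 80 h:
- fraction remaining at 5 days: 0.5^(120/80) = 35%;
- at 16.7 days: 0.5^5 = 3.1%;
- at 21 days: 0.5^6.3 = 1.3%.

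**4. Share of calendar time.**
- Extension window in protocol 9.4.2: 28 × 7 = 196 days; 21/(196 + 21) = 21/217 = 9.7%.
- All vibegron exposure, as SAP Section 3.1.2 counts it, for a 52-week man: 52 × 7 = 364 days; 21/(364 + 21) = 21/385 = 5.5%.

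Both figures apply to a man who completes treatment with *d* = 0. They describe time without a planned enquiry. They do not estimate missed events.

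**5. What reaches the TEAE tables under the SAP.** Take the EOS visit as the Week 52 visit on Day 365.

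| Last dose | Protocol 9.4.2: days after visit | SAP Table 2 | SAP 7.3 |
|---|---|---|---|
| Day 365 | 21 | min(370, 365) = Day 365, so 0 | Day 370, so 5 |
| Day 361 | 17 | min(366, 365) = Day 365, so 0 | Day 366, so 1 |

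The tabulated window therefore holds 0 to 5 days of unsolicited time, depending on which SAP passage is followed. SAP Section 9, which lists changes from the protocol, does not mention the move from 21 days to 5.

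**6. Do other provisions close the gap?** Section 8.4.3 starts from an AE already reported, and Section 8.3.4 starts from a laboratory value already judged significant. Neither plans a contact at which a man is asked about new events.

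**The case against.** The strongest reply is that the gap hardly touches the reported results. TEAE tables follow the SAP, so at most 5 unsolicited days count, and none under Table 2. A telephone call by itself would add events to the by-subject listings, which cover all reported AEs, but not to the TEAE tables beyond day 5. This stands. It limits the present effect, and it means the call must be paired with a decision on the cut-off. It does not remove the point: if the SAP were brought back to 21 days without a new contact, the added days would contain only observed or volunteered events.

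Second, known events are not abandoned. Section 8.4.3 follows them, and Section 8.4.1 requires later-learned SAEs reasonably related to the drug or to participation to be notified. This also stands, so the concern is confined to new-onset events.

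Third, Section 4.4 is a last-subject definition, and Section 8.4.1 states that the 21-day collection is additional to collection through the end of the study. The two can therefore be read together. That is fair; the gap for each man comes from the Schedule and Section 8.4.1, not from Section 4.4 alone.

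Finally, the study is single-arm and descriptive, with no safety testing, so no between-group comparison is distorted. That is true, but the incidence figures are themselves the main product of the study.

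**Conclusion.** The gap is real and modest. For up to 21 days after the final visit, and fewer when the last dose precedes it, the protocol counts a man as at risk without planning to ask him about new AEs. Under-ascertainment of new-onset events is the reasonable expectation, but the documents contain nothing from which to calculate its size. As the SAP stands, 0 to 5 of those days enter the TEAE tables. These figures assume that the final visit takes place and that the SAP's EOS visit is the Week 52 visit.

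A reader might infer more than the documents support:
- *That the whole period after stopping is unobserved for the roughly 33% assumed to drop out.* The Early Withdrawal visit includes AE review and can fall after the last dose, so the full 21 days is an upper bound.
- *That the outcome of an event leading to withdrawal is lost.* Such an event is already reported and is followed under Section 8.4.3.
- *That ascertainment is lowest just after early stopping.* Nothing in either document shows this.
- *That 9.7% measures bias.* It is a share of calendar time, and the SAP reports the proportion of men with events, not rates over person-time.
- *That the database could be locked too soon.* No passage ties the lock to Section 4.4.
- *That the SAP's safety follow-up proves a later contact was dropped.* It carries the Week 52 label, and the protocol schedule has no separate visit of that name. The footnote needs clarifying, but it is not evidence of a missing visit.

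**What to change.** 1. Add one AE/SAE telephone contact, of the kind already used at Week 44, at the end of the post-dose collection window that the protocol states. Apply it to completers and early withdrawals, and enter it in protocol Sections 1.3 and 10.7.
2. Reword protocol Section 4.4 and the EOS footnote to SAP Table 2 so that a man's participation ends no earlier than that contact.
3. Reconcile the TEAE cut-off in SAP Table 2 and Section 7.3, which differ on EOS, with protocol Section 9.4.2; otherwise list and justify the change in SAP Section 9.

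Step 3 is needed as well as step 2. With EOS moved to the call on Day 386 and the last dose on Day 365, Table 2 would close at min(370, 386) = Day 370, and days 6 to 21 would still fall outside the TEAE tables.

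The cost is one short call per man by existing site staff, about 300 calls at full enrollment, a last-subject end date about 3 weeks later, and small amendments to both documents. For any man already past his window when the change is made, the call would come too late; the study report should then say that new events after his last visit were not solicited.

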5.1. Inclusion Criteria

Subjects will be eligible for inclusion in this study only if all of the following criteria apply:

1. Has completed participation of the 24-week double-blind treatment period in Study URO-901-3005 and demonstrated compliance with the study procedures and study medication schedule in the opinion of the investigator.
2. Is capable of giving written informed consent, which includes compliance with the requirements and restrictions listed in the consent form.
3. Has ability to continue to receive a stable dose of BPH treatment with either a) alpha blocker monotherapy or b) alpha blocker + 5-ARI.
4. In the opinion of the investigator, is able and willing to comply with the requirements of the protocol, including completing study questionnaires and the Bladder Diary.

5.2. Exclusion Criteria

Subjects will not be eligible for inclusion in this study if any of the following criteria apply:

1. Experienced any SAE in Study URO-901-3005 that was reported as “possibly or probably related” to study treatment by the investigator.
2. Is a night-shift worker or plans to become a night-shift worker during the study.
3. Is using any prohibited medications as detailed in Section 10.6 (Appendix 7).
4. Is taking or using any medications to treat erectile dysfunction (ED) but is not using them on a regular schedule. If taking less than 2 times per week, ED medications with a short half-life such as sildenafil and vardenafil are allowed.
5. Has any planned procedures to treat ED (eg, implantation of a penile device) during the treatment period or has any planned prostate procedure.
6. Has a planned procedure to implant a sacral neurostimulation (SNS) or use of any posterior tibial nerve stimulation (PTNS) device.
7. Has coronary or neurovascular interventions planned during the duration of the study.

8. Has uncontrolled hyperglycemia (defined as fasting blood glucose > 150 mg/dL or 8.33 mmol/L and/or non-fasting blood glucose > 200 mg/dL or 11.1 mmol/L) based on most recent available lab results in Study URO-901-3005 or uncontrolled in the opinion of the investigator.
9. Has uncontrolled hypertension (systolic blood pressure of ≥ 180 mmHg and/or diastolic blood pressure of ≥ 100 mmHg) or has a resting heart rate (by pulse) > 100 beats per minute.
10. Has systolic blood pressures ≥ 160 mmHg but < 180 mmHg, unless deemed by the investigator as safe to proceed in this study and able to complete the study per protocol.
11. Subject has current evidence of any clinically significant condition, therapy, lab abnormality, or other circumstances that might, in the opinion of the investigator, confound the results of the study, interfere with the subject's ability to comply with study procedures, or make participation in the study not in the subject's best interest.

5.3. Lifestyle Considerations

Not applicable for this study.

5.4. Screen Failures

Not applicable for this study.

6. Study Drug

Subjects will retain the same subject identification number as was assigned in Study URO-901-3005.

6.1. Study Drugs Administered

Table 1 Summary of Study Drugs

Study Drug Name	Vibegron
Dosage Formulation	tablet
Identity of Formulation	75 mg
Route of Administration	oral
Dosing Instructions	once daily
Packaging and Labeling	Study drug will be provided in HDPE bottles with child-resistant caps. Each bottle will contain 32 tablets and will be labeled as required per country requirement.
Manufacturer	Patheon, Cincinnati, Ohio, US
Number and Timing of Drugs	Treatment Period: 1 tablet daily

The study drug will be supplied in bottles each containing 32 tablets (4-week treatment and 4-day extra supply) and labeled with the protocol number, lot number, expiration date, study drug name (vibegron 75 mg tablets) and number of tablets, directions for use, storage information, warning language (*Keep Out of Reach of Children. For Clinical Trial Use Only. To be used by qualified investigators only. Caution: New Drug—Limited by United States Law to Investigational Use.*), and the US Sponsor name and address. Immediately before dispensing the study drug, the investigator (or appropriately trained designee) will write the subject number, visit no. and the dispense date on the detachable panel of the label, which also includes the protocol number, bottle number and lot number.

Subjects will take 1 tablet of study drug (vibegron) once daily for up to 28 weeks.

6.2. Preparation/Handling/Storage/Accountability

Clinical supplies must be stored in a secure, limited-access location under the storage conditions specified on the label.

Receipt and dispensing of Study Treatment must be recorded by an authorized person at the study site.

Clinical supplies may not be used for any purpose other than that stated in the protocol.

The investigator is responsible for keeping accurate records of the clinical supplies received from the Sponsor or designee, the amount dispensed to and returned by the subjects, and the amount remaining at the conclusion of the study. These records will be monitored throughout the study.

For all sites, the local country Sponsor personnel or designee will provide appropriate documentation that must be completed for drug accountability and return.

6.3. Study Drug Compliance

Study drug compliance will be closely monitored by counting the number of tablets dispensed and returned. Before dispensing new study drug at applicable visits, study site personnel will make every effort to collect all unused study drug and empty bottles.

The study site will keep an accurate drug disposition record that specifies the amount of study drug administered to each subject and the date of administration.

6.4. Concomitant Therapy

The use of any concomitant medication, prescription or over-the-counter, is to be recorded on the subject's electronic case report form (eCRF) at each visit along with the reason the medication is taken, the dates of administration, and the dose.

6.4.1. Prohibited Drugs

Section 10.6 provides a listing of specific restrictions for concomitant therapy use during the study. If there is a clinical indication for any therapy that is specifically prohibited during the study, discontinuation from Study Treatment may be required. The investigator should discuss any questions regarding this with the Sponsor's representing Medical Monitor. The final decision on any supportive therapy rests with the investigator and/or the subject's primary physician. However, the decision to continue the subject on Study Treatment requires the mutual agreement of the investigator and the Sponsor's designated Medical Monitor.

Consult the Sponsor's designated Medical Monitor if there is any uncertainty regarding subject use of a particular drug or drug class.

